7.4. Laboratory Procedures

Not Applicable.

8. SUBJECTS COMPLETION/WITHDRAWAL

8.1. Completion Criteria

Subjects are considered to have completed the study if they:

- provided informed consent
- they are eligible
- completed all scheduled visits.

Clinical Study Protocol

Johnson & Johnson Vision Care, Inc.

8.2. Withdrawal/Discontinuation from the Study

A subject will be withdrawn from the study for any of the following reasons:

- Subject death during the study period
- Subject withdrawal of consent
- Subject not compliant to protocol
- Subject lost to follow-up
- Subject no longer meets eligibility criteria (e.g. the subject becomes pregnant)
- Subject develops significant or serious adverse events causing discontinuation of study lens wear
- Subjects who have experienced a Corneal Infiltrative Event (CIE)
- Investigator's clinical judgment regarding the subject safety reasons (that it is in the best interest of the subject to stop treatment)
- Subject misses any study visits
- Subject not compliant with study lens wear schedule
- Subject not successfully dispensed due to lack of efficacy and safety including poor vision, poor comfort, or unacceptable fit.

For discontinued subjects, the Investigator will:

- Complete the current visit (scheduled or unscheduled)
- Complete the Final Evaluation, indicating the reason that the subject was discontinued from the study.
- Record the spherocylindrical refraction with best corrected distance visual acuity
- Collect used test article(s) (worn or brought to the visit) from the subject and discard them, unless otherwise stated in Section 0
- Collect all unused test article(s) from the subject.

An additional subject will be enrolled if a subject discontinues from the study prematurely.

In cases where a subject is lost to follow-up, every possible effort must be made to contact the subject and determine the reason for discontinuation/withdrawal. The measures taken to follow up must be documented including two written attempts and a certified letter (or equivalent) as the final attempt.

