Trial Registration	This study will be registered on ClinicalTrials.gov by the Sponsor.
Test Article(s)	
Investigational Products:
 
 • senofilcon A contact lenses made with a novel manufacturing technology (Test) • senofilcon A contact lenses made with the current manufacturing technology (Control). •
Wear and Replacement Schedules	
Wear Schedule: daily wear
 
Replacement Schedule: daily disposable

Objectives	To evaluate the clinical performance of senofilcon A contact lenses made with a new manufacturing technology as compared to senofilcon A contact lenses made with the existing manufacturing technology.
Study Endpoints	
Co-primary endpoint(s):
 
 • Overall comfort after 1-week of lens wear • Overall quality of vision after 1-week of lens wear 
Secondary endpoint(s):
 
 • Monocular distance visual performance after 1-week of lens wear • Average daily wear time (in hour) after 1-week of lens wear 
Additional Endpoints:
 
 • Slit lamp findings • Subject reported ocular symptoms • Lens fitting characteristics • Lens wettability • Adverse events • Reasons for discontinuation • Lens damage

Clinical Study Protocol
Johnson & Johnson Vision Care, Inc.

Study Design	This study is a feasibility, multi-site, randomized, double-masked, 2×2 crossover design, 1-week dispensing study. Subjects will wear bilaterally both Test and Control lenses in a random order for 1-week each as a daily disposable modality with a wash-out period of 1 week between the wearing periods. See the flow chart at the end of the synopsis table for the schematic of the study visits and procedures of main observations (Figure 1).
Sample Size	Up to 133 eligible subjects will be enrolled and randomized into the study to ensure that approximately 120 subjects complete as cohort.
Study Duration	The study will last approximately 7 weeks and include an enrollment period of 3 weeks.
Anticipated Study Population	Healthy male and female volunteers (at least 18 and not more than 70 years old) who are habitual wearers of daily disposable contact lenses (we will aim for approximately 75% habitual silicone hydrogel daily disposable and approximately 50% habitual ACUVUE® OASYS 1-DAY wearers) and have a spectacle astigmatism of $\leq 0.75\text{D}$ in both eyes.

Clinical Study Protocol

Johnson & Johnson Vision Care, Inc.

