5.2. Masking

This is a double-masked study where subjects, investigators are masked to the identity of the study lenses during the study period. Every attempt will be made to keep the other clinical trial personnel involved in the study (e.g. data management, biostatistician) unaware of the identity of the study lenses.

The identity of the study lenses will be masked by over-labeling the blister packs with a label containing the study number, lot number, sphere power, expiration date and the randomization codes. Only the personnel involved in the over labeling and the statistician generating the randomization scheme will have access to the decode information translating the randomization codes into Test and Control groups. The Biostatistician performing the interim analysis will have access to the decode information to run the interim analysis. The medical monitor will also have access to the decode information in case breaking the mask is necessary for the urgent medical treatment of a subject.

Under normal circumstances, the mask should not be broken until all subjects have completed the study and the database is finalized. Otherwise, the mask should be broken only if specific emergency treatment/course of action would be dictated by knowing the treatment status of the subject. In such cases, the Investigator may, in an emergency, contact the medical monitor. In the event the mask is broken, the Sponsor must be informed as soon as possible. The date, time, and reason for the unmasking must be documented in the subject record. The Investigator is also advised not to reveal the study treatment assignment to the clinical site or Sponsor personnel.

Subjects who have had their treatment assignment unmasked are expected to return for all remaining scheduled evaluations. Subjects who are discontinued will not be replaced.

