1.24	White Light Lens Surface Wettability	Record the white light lens wettability of both lenses.
1.25	Surface Deposits	Record any front and back surface lens deposits.
Visit 1: Treatment 1 Lens Dispensing		
Step	Procedure	Details
1.26	Exit VA	Record subjects' distance Snellen visual acuity, OD, OS, and OU to the nearest letter.
1.27	Continuance	
For the subject to continue in the study, they must meet all three of the following criteria:
 
 • Visual acuity is 20/30 or better OD and OS

Clinical Study Protocol
Johnson & Johnson Vision Care, Inc.

Visit 1: Treatment 1 Lens Dispensing		
Step	Procedure	Details
		
 • The lens fit is acceptable OD and OS • Investigator approval. 
If the Investigator does not approve the dispensing of the first study lens, then the study is terminated for that subject.

1.28	Dispense	
The lenses will be dispensed for a 5-9 day wearing period. During this time, they are required to wear the lenses at least 5 days and at least 8 hours per day that they are worn.
 
 • Dispense enough lenses to last the subject to their scheduled follow-up visit. Do not dispense extras* • The lenses will be worn as daily wear/daily disposable only • Rewetting drops are permitted if needed • A patient instruction booklet will be provided • Subjects will be scheduled for their 1-week follow-up visit • Subjects should be instructed to wear the study lenses to the follow-up visit and bring their habitual correction with them. 
* Note: In the event a lens is lost or damaged, the subject will return to the clinical site for replacement. As much as reasonably possible, a damaged lens and packaging should be returned to the clinical site (wet, if possible) and then returned to the Sponsor. If lens damage is present, complete the Product Quality Complaint Form. The lens will be stored in labeled vial with saline, and clearly differentiated from the other worn lenses that will be shipped back to the Sponsor.

VISIT 2

Subjects should attend wearing their study lenses.

Visit 2: Treatment 1 Follow-Up Visit		
Step	Procedure	Details
2.1	Adverse Events and Concomitant Medications Review	Review any changes to the subject's medical history or concomitant medications from the previous study visit. Record any changes, and any adverse events.

Clinical Study Protocol
Johnson & Johnson Vision Care, Inc.

Visit 2: Treatment 1 Follow-Up Visit		

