14.2. Sample Size Justification

The plan is to enroll 130 subjects with a target completion of 120 subjects. This is a feasibility study and the sample size is chosen by the study responsible clinician and was not based on

Clinical Study Protocol

Johnson & Johnson Vision Care, Inc.

any statistical power analysis. The data collected for this study will be used to design future clinical trials. However, power calculation was conducted under different scenarios for the primary hypothesis testing to provide estimates on power with 120 subjects and both CLUE comfort and vision will be tested with 2-sided type I error of 0.05.

Table 6 provides a summary of power based on the hypothesis of non-inferiority for either CLUE comfort or vision score with 120 subjects to complete the study and two-sided Type I error of 0.05 with the assumptions for treatment effect (Test – Control) of CLUE score, standard deviation and intraclass correlation. The power calculation was conducted using the POWER procedure in SAS 9.4.

Table 6: Power Calculation for the Primary Hypothesis of either CLUE comfort or vision score (Non-inferiority) with Type I error of 0.05.

Mean Difference (Test - Control)	Standard Deviation	Total Sample Size (n/2 per sequence)	Intraclass Correlation			
			0.4	0.5	0.6	0.7
0	21	120	0.765	0.829	0.895	0.956
0	23	120	0.697	0.765	0.842	0.921
0	25	120	0.634	0.703	0.785	0.878
0	27	120	0.578	0.645	0.729	0.831
1	21	120	0.884	0.929	0.967	0.991
1	23	120	0.829	0.884	0.937	0.978
1	25	120	0.771	0.834	0.899	0.958
1	27	120	0.765	0.829	0.895	0.956

As shown in the Table 6, the study will be powered (power of 0.8 or higher) to show non-inferiority of the Test lens compared to the Control lens with respect to either CLUE comfort or vision score for the following scenarios: 1) the mean difference ≥ 0 , the standard deviation and an intraclass correlation ≥ 0.7 . 2) the mean difference ≥ 0 , the standard deviation ≤ 23 and an intraclass correlation ≥ 0.6 . 3) the mean difference ≥ 0 , the standard deviation ≤ 21 and an intraclass correlation ≥ 0.5 . 4) the mean difference ≥ 1 , the standard deviation ≤ 23 and an intraclass correlation ≥ 0.4 . 5) the mean difference ≥ 1 , the standard deviation ≤ 27 and an intraclass correlation ≥ 0.5 .

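### Section 8.2 requires withdrawal for any wear or protocol non-compliance, Section 10 calls the smaller shortfalls minor deviations, and neither is said to govern; read literally at Visit 2, 8.2 costs the ITT analysis period 2 data

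*Combined protocol and SAP*

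**What the plan says.** Section 8.2 opens its list with "A subject will be withdrawn from the study for any of the following reasons". Two of the reasons are "Subject not compliant to protocol" and "Subject not compliant with study lens wear schedule". Neither carries a threshold or a reference to Section 10.

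The wear requirement is in Section 7.2, steps 1.28 and 3.23: subjects receive lenses for 5 to 9 days and "they are required to wear the lenses at least 5 days and at least 8 hours per day that they are worn". Compliance is confirmed at Visit 2 (step 2.3), before the washout and the period 2 dispensing.

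Section 10 grades departures from that requirement. Wear for 4 or 10 days, or an average of 7 hours a day, is a minor deviation. Wear for 3 days or fewer or 11 or more, or an average of 6 hours or less, is a major deviation, and the subject is removed from the cohort.

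Section 14.3 defines ITT as all randomised subjects, whatever their withdrawal or deviation, with at least one observation. Per-protocol requires all visits completed and no substantial deviation, as judged by the trial cohort review committee. Section 14.5 runs the primary analysis on both sets, and Section 14.9 does not impute missing values in the main analysis.

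**The concern.** The two sections give different outcomes for the same subject. Someone who averages 7 hours a day in period 1 has a minor deviation under Section 10 and, by implication, goes on to period 2. Under the words of Section 8.2 that person has not met the protocol's wear requirement and must be withdrawn. Section 25 of the protocol does not exist to arbitrate, and no other section does: each of the seven sites in Table 1 would decide for itself.

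A non-inferiority comparison benefits from having ITT and per-protocol as two different views of the data. Per-protocol may drop subjects for how they wore the lens; ITT is there to show whether that matters. If deviators are withdrawn at Visit 2, ITT still counts them as members, but their period 2 comfort and vision scores are never collected. They also fail per-protocol, because they have not completed all visits. Both sets then carry a selection on wear time after randomisation. Wear time is itself a secondary endpoint and is not a term in the CLUE models.

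**Working it through.** **1. The same subject under each section (shortfall in period 1, found at Visit 2)**

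| Period 1 wear | Section 10 | Section 8.2 as worded |
|---|---|---|
| 5–9 days, at least 8 h/day | No deviation | Continues |
| 4 or 10 days, or 7 h/day average | Minor; no removal stated | Withdrawn |
| 3 days or fewer, 11 or more, or 6 h/day or less | Major; removed from cohort | Withdrawn |

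The middle row is the direct conflict. In the last row the question is whether removal from the cohort also ends follow-up. Under 8.2 a discontinued subject completes the current visit and the Final Evaluation, so Visits 3 and 4 do not take place. A shortfall first found at Visit 4 costs no CLUE score, because both periods have been observed by then.

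**2. The plan's own power figure**

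Section 14.2 says "The plan is to enroll 130 subjects with a target completion of 120 subjects". Table 6 gives power 0.765 for 120 completers, true difference 0, SD 23, intraclass correlation (ICC) 0.5. With a paired t test and margin 5:

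- SE = 23 × √(2 × (1 − 0.5)/120) = 2.100; noncentrality = 5/2.100 = 2.381; df = 119.
- One-sided 0.05 gives 0.765, which matches the table.
- One-sided 0.025, which corresponds to the planned two-sided 95% confidence interval, gives 0.656.

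That difference in alpha is a separate matter. The 0.025 basis is used below because it is the planned decision rule.

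**3. Effect of losing period 2 on precision**

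Inputs: 65 randomised per sequence (Table 1) and ICC 0.4 to 0.7 (Table 6). The documents give no rate of non-compliance, so 10 withdrawals, 5 per sequence, is an assumption for illustration.

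Model: fixed lens, sequence and period with compound symmetry. This is simpler than the planned model, which adds the baseline score and a random site effect and may select another covariance structure.

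Let n be the subjects per sequence with period 1 data, m those with both periods, and ρ the ICC. The variance of the lens difference, relative to no loss, is

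(1 − ρ)/2 + ((1 + ρ)/2) × (n/m).

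With n = 65 and m = 60, n/m = 1.0833:

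| ICC | Variance ratio, ITT | SE increase, ITT |
|---|---|---|
| 0.4 | 1 + 0.70 × 0.0833 = 1.0583 | 2.9% |
| 0.5 | 1 + 0.75 × 0.0833 = 1.0625 | 3.1% |
| 0.6 | 1 + 0.80 × 0.0833 = 1.0667 | 3.3% |
| 0.7 | 1 + 0.85 × 0.0833 = 1.0708 | 3.5% |

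In per-protocol the 10 drop out entirely: √1.0833 = 1.041, an increase of 4.1%.

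**4. Effect on power, same 10 withdrawals**

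At SD 23, ICC 0.5, true difference 0 (noncentral t, one-sided 0.025, df 128 less the number withdrawn):

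- No loss, 130 complete: SE = 23/√130 = 2.017, power 0.691.
- ITT with 10 contributing period 1 only: SE = 2.017 × 1.0308 = 2.079, power 0.665.
- Per-protocol with 120: SE = 2.100, power 0.656.

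Over SD 21 to 27 and ICC 0.4 to 0.7, the fall is 1.6 to 2.9 percentage points in ITT and 1.9 to 3.5 in per-protocol. The reference here is 130 completers. The plan expects 120, so the per-protocol case with 10 lost is the plan's own expectation, and the ITT case is slightly more precise than it.

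**The case against.** The best reply is that Section 10 is plainly the working rule. If every shortfall triggered withdrawal, its minor tier would have no purpose, and even a COVID-19 tele-visit, which Appendix E logs as a minor deviation, would end participation. The visit steps agree: step 2.3 only confirms compliance, step 2.16 sends the subject into washout, and the continuance checks at 3.9 and 3.22 contain no wear test. This stands as evidence of intent. It does not remove the mandatory wording of 8.2, and no order of precedence is given.

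The term wear schedule can also be read narrowly. The synopsis and Table 2 give it simply as daily wear, and Section 4.1 says subjects are advised on days and hours. That weakens reliance on the wear-schedule bullet alone. The general protocol bullet still covers the requirement in step 1.28.

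Cohort most naturally means the per-protocol set, since a cohort review committee decides that set and the synopsis speaks of completing as cohort. That is a fair inference, but Section 10 should say it.

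A reader might infer that the rule biases the trial toward a non-inferiority finding. The documents do not support that: they give no rate of short wear, no link between short wear and either lens, and no direction. The mixed model also keeps the period 1 and baseline scores, which adjusts for loss explained by them. A reader might equally infer a serious loss of power. The calculation shows otherwise, and Section 14.2 says the sample size was not set by power.

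**Conclusion.** The inconsistency is real and worth correcting, at modest weight. Section 8.2 and Section 10 prescribe different outcomes for minor wear deviators, and no text settles which applies. The consequence is conditional: it arises only if a site follows 8.2 literally, and only for non-compliance found before period 2. In that case ITT lacks the period 2 scores of subjects it is meant to retain, and it loses part of its independence from per-protocol.

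The number of subjects affected is unknown. The figure of about 3% on the ITT standard error rests on an assumed 10 withdrawals out of 130 and a simplified model; it is not an estimate of what this conflict would cause. The reason to act is that uncollected data cannot be recovered at analysis. It is not that a bias or a material loss of power has been shown. The study is labelled feasibility with exploratory hypotheses, which also keeps the weight down, although its data are meant to inform the design of later trials.

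**What to change.** In Section 8.2, stop treating wear-time or protocol non-compliance that raises no safety concern as a ground for study withdrawal. At minimum, limit these two grounds to the major deviations defined in Section 10, by cross-reference. State that off-schedule subjects continue through Visit 4 and contribute both periods to ITT. In Section 10, state that removal from cohort means exclusion from the per-protocol population and not withdrawal from the study.

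The cost is protocol wording only. No visits or procedures are added beyond those already scheduled for each subject.

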9. PRE-STUDY AND CONCOMITANT INTERVENTION/MEDICATION

Concomitant medications will be documented during screening and updated during the study. Disallowed medications for this study include: See Section 3.3

Concomitant therapies that are disallowed include: See Section 3.3

9.1. Systemic Medications

Certain systemic medications are known to have a higher likelihood to interfere with contact lens wear, chiefly by disrupting the tear film. A summary of disallowed medications is shown in Table 4. Subjects taking these medications on a continual, routine basis that have

Clinical Study Protocol

Johnson & Johnson Vision Care, Inc.

demonstrated successful contact lens wear for at least 6 months will generally be allowed to participate in this study. Subjects taking these medications on a routine basis but for less than 6 months will not be allowed to participate in the study.

NOTE: That subjects taking these medications on a temporary basis (e.g., antihistamines for seasonal allergy) will be allowed to participate if the medication has sufficient time to leave the body prior to the study. This is dependent on the half-life of the drug, body weight / fat, age, genetics, liver / kidney function, and metabolism of the subject. Given these unknowns, subjects taking the medications on a temporary basis must have ceased that medication at least 2 weeks prior to signing the informed consent.

Table 4: Disallowed systemic medications (less than 6 months of continual use).

Class of Drug	Common Indication(s)	Common Examples
Estrogens*	Menopause, osteoporosis, vaginitis	Vagifem, Estrace, Climara, Vivelle-Dot, Premarin, Minivelle, etc., ...
Antihistamines**	Allergic rhinitis, sedation, hives, allergic conjunctivitis, skin allergy, itching, motion sickness	Hydroxyzine, Promethagan, Phenadoz, Vistaril, Claritin, Zyrtec, Astepro, Astelin, Optivar, Pataday, Allegra, Benedryl, etc., ...
Anticholinergics	Irritable bowel syndrome, Parkinson's disease, peptic ulcer, cystitis, nasal congestion, cold symptoms, overactive bladder, COPD	Bentyl, Spiriva, Atrovent, Hyosyne, Levsin, Symax Fastab, Symax SL, Homax SL, Cogentin, Transderm Scop, etc., ...
Beta-blockers	Hypertension, angina, heart attack, migraine, atrial fibrillation, adrenal cancer, essential tumor, glaucoma	Toprol XL, Lopressor, Tenormin, Propranolol, Timoptic, Trandate, Inderal LA, etc., ...
Psychotropics	Antipsychotic (schizophrenia, mania), antidepressant, antiobsessive, antianxiety, mood stabilizer, stimulants (ADHD)	Zoloft, Celexa, Prozac, Lexapro, Effexor, Cymbalta, Ativan, Xanax, Desyrel, Wellbutrin, etc., ...
Vitamin A analogs	Cystic acne	Isotretinoin

*Contraceptive medication not included in this category

**Antihistamines allowed if taken continuously and demonstrated successful wear while taking the medication, or if they stopped taking the medication for at least 2 weeks prior to enrollment

Clinical Study Protocol

Johnson & Johnson Vision Care, Inc.

10. DEVIATIONS FROM THE PROTOCOL

Investigator will notify study sponsor upon identification of a protocol deviation. Protocol deviations must be reported to the sponsor within 24 hours after discovery of the protocol deviation. The Investigator will report deviations per IRB/IEC requirements. All deviations will be tracked and corrective actions implemented as appropriate.

If it becomes necessary for the Investigator to implement a deviation in order to eliminate an immediate hazard to the trial subject, the Investigator may implement the deviation immediately without notification to the sponsor. Within 24 hours after the implemented deviation, the Investigator must notify and provide the rationale to the Sponsor and, as required, the IEC/IRB.

If the deviation potentially impacts the safety of patient or changes the technical integrity of the study then it must be reported to IEC/IRB. This is a "Major Deviation".

Minor deviations have no substantive effect on patient safety or technical integrity of the study. They are often logistical in nature. The informed consent must also not be contradicted by the deviation.

Protocol waivers are prohibited

Subjects will be dispensed study lenses at visit 1 and visit 3 for 5-9 days of wear. If the subject wears the lenses for 4 days or 10 days this will be a minor deviation. If the subject wears the lenses for 3 or less days or 11 or more days this will be a major deviation and the subject will be removed from cohort.

The washout between visit 2 and visit 3 is 7-9 days. If the washout is instead 4-6 days or 10-15 days, this will be a minor deviation. If the washout is 3 or less days and 16 or more days, this will be a major deviation and the subject will be removed from cohort.

While dispensed, the study lenses are to be worn 8 hours a day. If the average wear time is 7 hours a day this will be a minor deviation. If the average wear time is 6 hours or less a day this will be a major deviation and the subject will be removed from cohort.

